14.3.10 Analysis of patient-reported outcomes

POEM and DLQI will be summarised by treatment group and visit using descriptive statistics. Data will be presented for the full analysis set.

The patient-reported outcomes collected daily in the eDiary (Worst Daily Pruritus NRS, Eczema-related Sleep NRS, and Patient Days of Topical Treatment Use) will all be summarised over time by treatment group using descriptive statistics. Data will be presented for the full analysis set.

The change from baseline to Week 16 in Eczema-related Sleep NRS weekly average and POEM will be summarised by treatment group and domain, where applicable, and analysed according to the primary analysis of the secondary estimand for the continuous key secondary endpoints. For the Eczema-related Sleep NRS score, the mean over the last 7 days prior to randomisation (Day -6 to Day 0) will be used as the baseline value.

14.3.11 Exploratory analyses

To further support the evaluation of the primary, key secondary, and secondary endpoints, the same endpoints will be evaluated at each scheduled visit/assessment up to the week specified below:

- EASI75 at each scheduled assessment up to Week 14.
- IGA 0/1 at each scheduled assessment up to Week 14.
- Change in SCORAD from baseline to each scheduled assessment up to Week 14.
- Change in Worst Daily Pruritus NRS (weekly average) from baseline to each scheduled assessment up to Week 15.
- Change in DLQI score from baseline to each scheduled assessment up to Week 12.
- Reduction of Worst Daily Pruritus NRS (weekly average) ≥ 4 from baseline to each scheduled assessment up to Week 15.
- Change in Eczema-related Sleep NRS (weekly average) from baseline to each scheduled assessment up to Week 15.
- Change in POEM score from baseline to each scheduled assessment up to Week 12.

For the binary endpoints above, the treatment difference and the corresponding 95% CI will be presented at each scheduled visit/assessment using the same approach as applied for the primary analysis of the primary estimand for the primary endpoints. For continuous endpoints, the approach used for the primary analysis of the secondary estimand for key secondary endpoints will be applied.

For the binary endpoints, the same Mantel-Haenszel method as for the Week 16 assessment will be applied. For the continuous endpoints, the repeated measurements model already described previously for the Week 16 assessments facilitates that the treatment differences and 95% CIs can be derived for each visit/assessment in the same analysis that already will be made for the corresponding Week 16 assessments.

14.3.12 Analysis of safety

The analysis of safety will be based on the safety analysis set.

14.3.12.1 Adverse events

AEs will be coded during the course of the trial according to Medical Dictionary for Regulatory Activities (MedDRA). AEs will be presented by PT and primary system organ class (SOC).

Treatment-emergent AEs will be summarised; however, all AEs recorded during the course of the trial will be included in subject data listings. An event will be considered treatment-emergent if started after the first use of IMP or if started before the first use of IMP and worsened in severity after first dose of IMP. The tabulations described in the following will only include the treatment-emergent events. In each of the tabulations, AEs are defined by MedDRA PTs within primary SOC.

An overall summary of the number of events and the number (percentage) of subjects with any treatment-emergent AEs, deaths, SAEs, premature discontinuations from the trial due to AEs, treatment-related AEs, and severe AEs will be presented.

The number of AEs and number of subjects with each type of AEs will be tabulated by treatment group.

The severity for each type of AE will be tabulated by treatment group.

The causal relationship to IMP for each type of AE will be tabulated by treatment group. Related AEs are defined as AEs for which the investigator has not described the causal

relationship to IMP as ‘not related’. The number of related AEs and the number of subjects with each type of related AE will be tabulated.

The causal relationship to AxMP (TCS) for each type of AE will be tabulated by treatment group. Related AEs are defined as AEs for which the investigator has not described the causal relationship to AxMP (TCS) as ‘not related’. The number of related AEs and the number of subjects with each type of related AE will be tabulated.

SAEs will be evaluated separately, and a narrative will be given.

AESIs and AEs leading to withdrawal from trial or permanent discontinuation of IMP will be tabulated and listed, no narratives will be given unless the events are considered as SAEs.

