During the initial treatment period in the AD pool, the frequency of serious adverse events (SAEs) was lower for tralokinumab (2.1%) than for placebo (2.8%). The majority of SAEs in both treatment groups were severe events, with similar frequencies for tralokinumab (1.5%) and placebo (1.7%). The frequencies of SAEs leading to permanent discontinuation of IMP were low and similar for tralokinumab (0.6%) and placebo (0.8%). The outcome of the majority of SAEs were recovered/resolved for both tralokinumab (32 of 38 events) and placebo (16 of 22 events).

During prolonged treatment with tralokinumab with or without TCS from 16 up to 52 weeks, the safety profile was consistent with the initial 16-week treatment period based on overall frequencies of AEs, SAEs, severe AEs, and AEs leading to permanent discontinuation of IMP as well as the patterns of event types within each of these AE categories.

Tralokinumab-treated subjects had a greater mean initial increase from baseline in eosinophil count compared with subjects treated with placebo. However, the increase in the tralokinumab-treated subjects was transient, and mean eosinophil counts returned to baseline

during continued treatment. No other clinically significant biochemistry parameters were identified from the completed phase 3 trials.

Data from the trials with tralokinumab in AD showed that the incidence rate of ADA and neutralising antibodies after 16 weeks of treatment was low and similar for tralokinumab and placebo, confirming the low immunogenicity of tralokinumab.

Overall, there were no indications that treatment with tralokinumab was associated with a higher risk of the following safety areas: skin infections requiring systemic treatment, eczema herpeticum, severe and serious infections (including any clinical endoparasitosis, opportunistic infections, and tuberculous infections), malignancies, anaphylaxis, serious allergic reactions, and immune complex disease. However, AEs of conjunctivitis, keratitis, and injection site reactions were more frequent with tralokinumab than placebo.

Thus, tralokinumab has a favourable safety profile, without any important risks identified in the clinical trials conducted to date.

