13.3 Reporting of adverse events

AEs reported by the subject or observed by the investigator must be recorded on the AE form of the eCRF and should be described in the following manner:

The *AE term* must be in precise English medical terminology (that is, not necessarily the exact words used by the subject). Whenever possible, a specific diagnosis should be stated (for example ‘allergic contact dermatitis’).

The *duration* of the AE must be reported by the start date and stop date of the event (if the event is ongoing it will also be recorded). In addition, it must be recorded whether the AE started on the same day as the IMP administration (i.e. before or after dosing).

AEs must be classified in terms of severity, causality, and outcome according to the definitions in [Appendix 2](#). For events not considered related to IMP, the causal relationship to the use of AxMP should be evaluated using the same definitions as for the IMP.

Action taken with trial treatment: any action taken with IMP or AxMP as a consequence of the AE must be recorded (dose not changed, dose reduced, dose increased, drug interrupted, drug withdrawn, not applicable, unknown).

Other action taken: any other action taken as a result of the AE must be recorded (none, concomitant medication, concurrent procedure).

Withdrawn from trial due to this AE: it must be recorded whether the AE led to withdrawal from the trial.

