13.4.1 Investigator reporting responsibilities

Any SAE must be reported to LEO Pharma K.K. on the (paper) SAE form within 24 hours of first knowledge. This report should contain an assessment of available information on seriousness, severity, causal relationship to the IMP, AxMP, or trial procedure, the action taken, the outcome to date, and a narrative description of the course of the event.

By signing and dating the SAE form, the investigator acknowledges that he/she is aware of the SAE and has assessed the causal relationship of the IMP(s) and any of the other medications to the SAE.

The actual reporter, if not the investigator, should also sign and date the SAE report.

The completed SAE form must be faxed or scanned and e-mailed to Pharmacovigilance at LEO Pharma K.K. using the e-mail address or fax number below:

Pharmacovigilance at LEO Pharma K.K.

E-mail address: [contact]

[contact]

If relevant, the investigator will enclose other information with the SAE form, such as anonymised reports of diagnostic procedures, hospital records, autopsy reports, etc.

Additionally, Global Safety at LEO Pharma may request further information in order to fully assess the SAE. The investigator must forward such information to LEO Pharma K.K. upon request by fax or e-mail (see contact details above).

The investigator must notify the local IRB(s)/IEC(s) of SAEs, as required by current applicable legislation for the concerned country.

SAEs occurring after the completion of the clinical trial, including post-treatment follow-up (i.e. after the last safety follow-up visit at Week 20), should not be routinely sought or recorded.

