Appendix 2: Classification of adverse events

Severity

The *severity* of the AE should be described in terms of mild, moderate, or severe according to the investigator's clinical judgement.

Mild	An AE that is usually transient and may require only minimal treatment or therapeutic intervention. The event does not generally interfere with usual activities of daily living.
Moderate	An AE that is usually alleviated with additional specific therapeutic intervention. The event interferes with usual activities of daily living, causing discomfort but poses no significant or permanent risk of harm to the subject.
Severe	An AE that interrupts usual activities of daily living, or significantly affects clinical status, or may require intensive therapeutic intervention.

If the severity of an AE worsens, a new AE should be recorded.

Causality

The *causal relation* of the AE to the use of the IMP should be described in terms of probably, possibly, or not related according to the investigator's clinical judgement.

Probably related	
Follows a reasonable temporal sequence from administration of the IMP.
 
Could not be reasonably explained by the subject's clinical state, environmental or toxic factors or other therapies administered to the subject.
 
Follows a known pattern of response to the IMP.
 
Disappears or decreases on cessation or reduction in dose of the IMP.
 
Reappears or worsens upon re-challenge.

Possibly related	
Follows a reasonable temporal sequence from the administration of the IMP.
 
Could also be reasonably explained by the subject's clinical state, environmental or toxic factors or other therapies administered to the subject.
 
Follows a known pattern of response to the IMP.

Not related	
Does not follow a reasonable temporal sequence from administration of the IMP.
 
Is better explained by other factors like the subject's clinical state, environmental or toxic factors or other therapies administered to the subject.
 
Does not reappear or worsen upon re-challenge.
 
Does not follow a known pattern of response to the IMP.

For events not considered related to IMP using the criteria above, the causal relationship to the use of AxMP should be evaluated using the same definitions as for the IMP.

Outcome

The *outcome* of the event according to the investigator's clinical judgement should be classified using the categories below.

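### TCS causality is requested only for AEs judged unrelated to IMP, yet TCS-related is defined by negation, so read literally an unrated IMP-related AE counts as TCS-related

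*Protocol*

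**What the plan says.** **Collection.** Protocol 13.3 states: "For events not considered related to IMP, the causal relationship to the use of AxMP should be evaluated". The rating scale is the one used for the IMP. Appendix 2 repeats the condition: "For events not considered related to IMP using the criteria above, the causal relationship to the use of AxMP should be evaluated". The scale has three levels; causality "should be described in terms of probably, possibly, or not related according to the investigator's clinical judgement". No level is provided for an event whose relation to TCS was not assessed.

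**Exception.** For SAEs, Protocol 13.4.1 asks that the paper report cover "seriousness, severity, causal relationship to the IMP, AxMP, or trial procedure, the action taken" and other items, with no condition on the IMP rating.

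**Analysis.** Protocol 14.3.12.1 states: "The causal relationship to AxMP (TCS) for each type of AE will be tabulated by treatment group". It then defines the related events as "AEs for which the investigator has not described the causal relationship to AxMP (TCS) as" 'not related'. The table is not restricted to events that have a TCS rating. The same section defines IMP-related events by the same negative construction.

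**SAP.** Section 6.7.1 covers the assignment of AEs to periods, sort order and a search for injection site reactions. It says nothing about TCS causality.

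**The concern.** A definition by negation is safe when the variable is collected for every event, because a blank is then a true omission and counting it as related is conservative. Here the variable is collected conditionally, so blanks are expected by design, and they fall on the events already attributed to the other product.

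The safety objective concerns tralokinumab used together with TCS, and attribution to each product is a planned output. Protocol 5.2 reports that "AEs of conjunctivitis, keratitis, and injection site reactions were more frequent with tralokinumab than placebo". To the extent that investigators rate such events as IMP-related, the literal rule would copy them into the TCS-related table, possibly more often in the tralokinumab arm. An injection site reaction could be listed as related to a cream. The opposite convention, treating blanks as 'not related', would also be wrong: an event plausibly due to both products would never enter the TCS table.

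**Working it through.** The plan states no figure to reproduce. The check is to apply the definition in 14.3.12.1 to each combination of ratings that 13.3 and Appendix 2 can produce.

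| IMP rating | TCS rating | Result under 14.3.12.1, read literally | TCS relation affirmed by the investigator? |
|---|---|---|---|
| Not related | Not related | Not TCS-related | No |
| Not related | Possibly or probably | TCS-related | Yes |
| Not related | Requested but missing | TCS-related (conservative default) | No |
| Possibly or probably | Not requested, blank | TCS-related | No |

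The first two rows work as intended. The third is a defensible default for a genuine omission. The fourth is the fault: the event is labelled TCS-related although the protocol did not ask the question. An SAE with a TCS rating on the SAE form would follow that rating and avoid the fourth row, provided that rating feeds the table, which the documents do not say.

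**Is the gap closed elsewhere?** SAP 6.7.1 has no rule for a missing TCS rating. SAP 6.8.3 deals with incomplete dates and times. SAP 6.8.7 sends missing values back to the protocol. Protocol 14.3.17 sends them to the individual analysis sections, which here means 14.3.12.1 again. The references form a loop with no rule in it.

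**Size.** The number of misclassified events equals the number of non-serious IMP-related AEs with no TCS rating. The documents give no such rate, so what follows is illustration only. Protocol 14.1 plans about 100 subjects randomised 1:1, hence about 50 per arm.

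- Assumed share of subjects with an IMP-related AE, tralokinumab/placebo, and the most that would be relabelled:
  - 10%/5%: 50 × 0.10 = 5 and 50 × 0.05 = 2.5.
  - 20%/10%: 50 × 0.20 = 10 and 50 × 0.10 = 5.
  - 30%/15%: 50 × 0.30 = 15 and 50 × 0.15 = 7.5.
- The resulting arm differences of 5, 10 and 15 percentage points are simply the differences that were assumed.
- With a figure from the documents: Protocol 5.2 gives conjunctivitis in 5.4% on tralokinumab and 1.9% on placebo. Then 50 × 0.054 = 2.7 and 50 × 0.019 = 0.95, a gap of 1.75 subjects. That holds only if every case were non-serious, rated IMP-related and left without a TCS rating.

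**The case against.** The strongest reply is that the text does not settle what the table will show. The eCRF is not in the documents; the TCS field might be open for every AE or filled by default. Sections 13.3 and Appendix 2 say when TCS causality should be evaluated but do not forbid rating it otherwise. One can also argue that a definition phrased around what the investigator described presupposes a rating, so that unrated events lie outside it. This stands as a limit on prediction. It does not rescue the rule, because neither document states that restriction and the table is planned for all types of AE.

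Second, misreading is partly guarded against. Causality to IMP is tabulated separately and all AEs are listed. Conjunctivitis and keratitis are AESIs with their own tabulation, and injection site reactions have a dedicated search in SAP 6.7.1. That is fair, but it helps a reader detect a wrong count and does not make the count right.

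Third, the impact is limited. There is no formal testing (Protocol 14.3.5), both arms receive TCS, and neither safety endpoint (number of treatment-emergent AEs per subject, treatment-emergent ADA) uses causality. This stands in full.

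Fourth, a rule that no blank may ever count as related would go too far: it would also remove the conservative default for ratings that were due but not entered. This stands, and the fix below respects it.

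**Conclusion.** The collection rule and the analysis definition do not fit together. As written, the definition in 14.3.12.1 classifies a non-serious IMP-related AE with no TCS rating as TCS-related without any assessment of TCS. This is a stated rule that misclassifies, not merely a missing detail, and nothing in the SAP repairs it.

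A reader might go further and infer that every IMP-related AE will appear as TCS-related, or that the table will show a false excess of TCS reactions on tralokinumab. The documents do not support either. The first depends on how the eCRF field is built and on blanks being programmed literally. The second depends also on IMP-related AEs being more frequent on tralokinumab, for which no rate is given. In Protocol 5.2 overall AE frequencies were similar (66% on tralokinumab, 67% on placebo), and dermatitis atopic was less frequent on tralokinumab (15% against 26%).

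The size therefore cannot be computed. The consequence is confined to descriptive safety tables; no efficacy result and no safety endpoint is affected. It is still worth correcting, because attribution to each product is a planned output and the correction is cheap.

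**What to change.** **Preferred.** Amend 13.3 and Appendix 2 so that the investigator rates causality to IMP and to AxMP separately for every AE. The definition by negation then works for TCS as it already does for IMP. The cost is one extra rating per AE.

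**If collection can no longer change.** Add to SAP 6.7.1, before unblinding, that:

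- the TCS-related definition applies only to AEs for which a TCS rating was requested or given, which keeps SAEs rated on the SAE form;
- IMP-related AEs with no TCS rating are shown in a separate category, 'not assessed (IMP-related)';
- counting a blank as related is kept only where the rating was requested (the AE was judged not related to IMP, or is an SAE) and is missing.

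The cost is one extra table category and a few sentences. No endpoint, efficacy analysis or sample size changes.

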14.3.12.2 Vital signs

The change in vital signs (resting blood pressure, pulse, and body temperature) from baseline to each visit will be summarised by visit and treatment group as mean, standard deviation (SD), median, minimum, and maximum values.

14.3.12.3 Clinical laboratory evaluation

The change in each of the laboratory parameters from baseline to each visit will be summarised by visit as mean, SD, median, minimum, and maximum values for each treatment group.

Laboratory parameters will be classified as ‘low’, ‘normal’ or ‘high’, depending on whether the value is below, within, or above the reference range, respectively. A shift table will be produced showing the categories at baseline against those at end of treatment. Subjects with laboratory parameters outside the reference range will be listed.

14.3.13 Pharmacokinetic analysis

All the PK samples in the trial are trough samples. The trough concentration (C_{trough}) will be listed by treatment group and descriptive statistics will be applied.

14.3.14 Anti-drug antibodies

The presence of treatment-emergent ADA from baseline to Week 16 is a secondary endpoint included to assess the safety and tolerability (immunogenicity) of tralokinumab in combination with TCS.

ADA status (positive versus negative) at each visit will be summarised by treatment group. If considered relevant, descriptive statistics including number of subjects, mean, SD, median, 1st quartile, 3rd quartile, and range of the actual ADA titres by treatment group and visit will be provided. The ADA status across the trial for each subject (positive versus negative) will also be classified and summarised by treatment group.

The association of ADA status across the trial (positive versus negative) with AEs/SAEs may be evaluated. In addition, the association of ADA titres (\geq median titre in positive subjects versus $<$ median titre) with AE/SAEs may be evaluated for ADA-positive treated subjects only.

The ADA status will be categorised as follows:

- Positive
 1. Pre-existing: ADA positive at baseline, no post-baseline ADA response \geq 4-fold over baseline titre level, and at least 1 non-missing post-baseline ADA assessment.
 2. Treatment-boosted: ADA positive at baseline and at least 1 post-baseline ADA response \geq 4-fold over baseline titre level.
 3. Treatment-emergent: ADA negative or missing at baseline and at least 1 positive post-baseline ADA response.
- Perishing
 4. ADA positive at baseline, all post-baseline ADA assessments negative.
- Negative
 5. ADA negative or missing at baseline, all post-baseline ADA assessments negative.
- No post-baseline ADA assessment.

For subjects who develop ADA and are considered treatment-boosted or treatment-emergent, the IGA score, change in EASI at end of treatment, and titre information will be listed.

Evaluations of neutralising antibodies will be conducted on those serum samples that test positive for ADA. The test sample is deemed positive or negative for the presence of neutralising antibodies to tralokinumab relative to a pre-determined (in assay validation), statistically derived cut point.

14.3.15 Interim analysis

No interim analysis is planned.

14.3.16 General principles

All CIs will be presented with 95% degree of confidence, unless otherwise specified.

An observed-cases approach will be used for tabulations of data by visit (that is, involving only those subjects who attended each specific visit).

Categorical data will be summarised using the number and percentage of subjects in each category and treatment group. Continuous data will be summarised using the mean, median, SD, minimum and maximum values.

All the analyses specified in the protocol will be reviewed in relation to the blinded data actually obtained and the statistical analysis plan will be finalised before breaking the randomisation code.

Any changes from the statistical analyses planned in this clinical trial protocol will be described and justified in a protocol amendment, the statistical analysis plan update and/or in the CTR, dependent on the type of change.

